## E-5 Data Analysis Considerations for the Two Co-Primary Hypotheses

The analysis of the primary endpoint will follow the methods described in sections [3](#) (stratification) and [8.1](#) (Gray's test for the primary comparisons and Fine-Gray models to estimate RRRs and 95% CIs, stratified by study site pharmacy). The following additional considerations apply to the AZD7442 study:

- The same stratification will be used for testing both co-primary hypotheses. Using blinded baseline data available on January 21, 2022, the strata were determined as follows. To avoid sparse strata, study pharmacies were pooled following the principles described in section [3](#). Seven strata, each including at least 20 participants in the nAb-negative subgroup, were formed using large sites where possible and combining small sites with each other or with a larger site where that was not. In addition, some very small sites that only enrolled participants who were nAb-positive were combined with one of the 7 strata. For the 99 sites that enrolled at least one participant, the 7 strata will be defined as follows: 1) 3 strata for the 3 U.S. sites that enrolled at least 20 nAb negative participants; 2) 1 stratum for all other U.S. sites; 3) 1 stratum for sites in Denmark, Greece, the United Kingdom, and Singapore; 4) 1 stratum for sites in Spain; and 5) 1 stratum for sites in Uganda.

- No participants were randomized in disease severity stratum 2 (defined in section 1.2; in particular, stratum 2 included participants requiring invasive mechanical ventilation or ECMO). Therefore, the originally planned stratification of analyses by disease severity stratum can't be carried out. Early in the trial, participants requiring non-invasive ventilation (NIV) or oxygen from a high-flow nasal cannula (HFNC) also were excluded. Beginning July 19, 2021, eligibility was expanded to include participants requiring NIV or HFNC. Considering this expansion of eligibility criteria, a sensitivity analysis will be carried out using a Fine-Gray model that only stratifies by oxygen requirements at baseline. A sensitivity analysis without any stratification will also be carried out.
- A subgroup analysis by calendar date of enrollment will also be carried out (2 subgroups: participants enrolled before July 19, 2021 and at or after July 19, 2021). The cut-point was chosen because on July 19, 2021, the first patient who required HFNC or NIV was enrolled after eligibility was expanded to include such patients.

If the primary comparison of AZD7442 versus placebo for time to sustained recovery shows a significant treatment effect in nAb-negative participants, then major safety, efficacy, and subgroup analyses will be conducted for the nAb-negative participants as well as for the full study cohort.

## E-6 Interim Monitoring Guidelines

There are 2 changes to the interim monitoring guidelines described in Section 10.3 of this SAP:

- The information fraction for the Lan-DeMets spending function will be based on the target of 1,228 sustained recoveries, not 843.
- As part of the broad assessment of risk/benefit, the DSMB should consider the findings in nAb negative and nAb positive subgroups. For participants who are nAb negative, greater benefit with the investigational agent is hypothesized.

**Comment:** The antibody status at baseline was unknown for a large proportion of participants until late in the trial. Therefore, separate interim monitoring boundaries were not planned for this subgroup.

## E-7 Subgroup Analyses by Vaccine and Immunosuppression Status

The hypotheses in this subsection were developed for the comparison of AZD7442 (a long-acting antibody combination) versus placebo, but apply more generally to monoclonal antibodies and antiviral agents. The outcomes, and the specific statistical models used for the subgroup analyses for each of the outcomes were described in Section 9.1.

The subgroup analyses by vaccination status and immunosuppression status address the following hypothesis:

**Hypothesis 1:** AZD7442 will have greater efficacy in non-vaccinated, compared to fully or partially vaccinated, study participants.

**Hypothesis 2:** AZD7442 will have greater efficacy in immunosuppressed, compared to not immunosuppressed, study participants.

For vaccination status, three mutually exclusive subgroups will be formed according to the current CDC definition of vaccination status:

- a. **Fully-vaccinated:** Subjects who have onset of acute symptoms of SARS-CoV-2 infection at least 14 days after receiving:
  - i. the **second** dose of a two-dose SARS-CoV-2 vaccine series, OR
  - ii. a **single** dose of the Janssen (J&J) SARS-CoV-2 vaccine
- b. **Partially-vaccinated:** Subjects who have:
  - i. received **only one dose** of two-dose SARS-CoV-2 vaccine series, OR
  - ii. onset of acute symptoms of SARS-CoV-2 infection prior to 14 day following the administration of the **second** dose of a two-dose SARS-CoV-2 vaccine series or a **single** dose of the Janssen (J&J) SARS-CoV-2 vaccine
- c. **Non-vaccinated:** Never received any dose of a SARS-CoV-2 vaccine.

**Comment:** Information about booster doses is not available.

Subgroup analyses by immunosuppressive status will consider three mutually exclusive subgroups, as defined below:

- **Immunosuppressed**, defined as any of the following:
  - Receiving antirejection medication (after solid or stem cell transplant)
  - Receiving biologic medicine to treat autoimmune disease or cancer, excluding IL-1 inhibitors, IL-6 inhibitors, Janus kinase inhibitors, and TNF inhibitors
  - HIV or other immunosuppressive condition
- Receiving any of the following immunomodulators: IL-1 inhibitors, IL-6 inhibitors, Janus kinase inhibitors, or TNF inhibitors, but not “immunosuppressed” as defined above
- None of the above

Data from TICO and other studies have shown that baseline vaccination status and immunosuppressive status are correlated; in particular, in our study population of patients who are hospitalized with COVID-19 pneumonia, the proportion of immunosuppressed patients is higher among those who are *fully vaccinated* compared with those who are unvaccinated. In addition, studies have found that the decline over time in immunity varies between vaccines. In order to address potential confounding between vaccination status, immunosuppressive status, and type of vaccine, models for subgroup analyses by vaccination status will include immunosuppressive status and type of vaccine (mRNA versus other) as covariates. Similarly, models for subgroup analyses by immunosuppressive status will include vaccination status and type of vaccine as covariates.

The following **exploratory analyses** will be conducted if the sample size is large enough for meaningful analyses:

- Subgroups will also be formed by combinations of *vaccination status and vaccine type* (4 categories: not vaccinated; partially vaccinated; fully vaccinated with non-mRNA vaccine; fully vaccinated including at least one mRNA vaccine in the sequence). Models for this subgroup analysis will be adjusted for immunosuppressive status.

- Subgroups will be formed by the bivariate combinations of *vaccination status and immunosuppressive status*.

In order to facilitate the interpretation of the results of the subgroup analyses, baseline levels of antibodies, antigen, and SARS-CoV-2 RNA will be summarized by vaccination status and by immunosuppressive status. These biomarkers include the following:

- SARS-CoV-2 antibody levels (nAb by GenScript, anti-N by BioRad, and anti-Spike IgG antibody levels by Quanterix assays)
- SARS-CoV-2 antigen levels in plasma
- Viral RNA by midturbinate swabs

See [Appendix F](#) for details on assays and outcome measures.

## E-8 Subgroup Analyses by Viral Strain

Between March 1 and September 30, 2021, 1455 participants were randomized to AZD7442 or placebo. The enrollment period included time periods both prior to and after the emergence of the Delta variant. Higher levels of plasma nucleocapsid antigen at baseline were observed during enrollments in July-September compared to enrollments in March-June, which coincided with the emergence and global replacement of the Alpha/other viral variants with the Delta variant. Observational studies suggest worse clinical outcome from being infected with the Delta than the Alpha viral variant.

**Research Question 1:** Does the treatment effect of AZD7442 versus placebo differ based on the viral strain that the participant is infected with?

**Hypothesis:** The benefit of AZD7442 differs between participants who were infected with the Delta variant versus those who were infected with other viral variants.

*Justification:* The AZD7442 nMAb combination binds to non-overlapping epitopes on the SARS-CoV-2 Spike protein, presumably decreasing viral replication and dissemination by blocking the ability of the Spike protein to bind to host cells expressing ACE2. As such, participants who were infected with the Delta variant versus those who were infected with other viral variants may benefit more from treatment with ADZ7442. This may be particularly pronounced in the subset of participants who have not yet mounted their own endogenous neutralizing antibody response.

An alternate hypothesis is that the dose of AZD7442 is better able to contain viral replication among persons infected with a less virulent viral strain, and hence the relative benefit from using AZD7442 could be more pronounced among participants infected with non-Delta than Delta viral variants.

*Statistical analyses:*

To address the hypothesis of a differential treatment effect, the investigational agent will be compared versus placebo in subgroups by SARS-CoV-2 variant (Delta versus other), and tests for differential treatment effects across the subgroups will be performed by testing for

interactions between the treatment and subgroup indicators. Subgroup analyses will be performed for time to sustained recovery (primary efficacy outcome) and key safety outcomes, including the composite outcomes of *grade 3 or 4 AEs, SAEs, organ failure, serious infections, or death* through Day 28; *SAEs, organ failure, serious infections, or death* through Day 90; and death through Day 90. Statistical methods for the subgroup analyses are described in Section 9.1.

Because the composition of the study population may have changed over time, including an increase in the proportion of participants infected with the Delta variant, an increase in the proportion of vaccinated persons in the general population, and changes in the population with respect to supplementary oxygen requirements, models for these subgroup analyses will also consider adjustment for vaccination status, and for supplementary oxygen requirements at study entry (categories of the ordinal pulmonary outcome).

### **Research Question 2:** What is the effect of specific mutations?

AZD7442 is a combination therapy targeting non-overlapping epitopes in the RBD. While mutations found in variants can impact the binding of either one of the nMAbs (including at positions R346, K444, V445, G446, N450, L452 G476, E484, Q493K) the combination is hypothesized to retain activity. Nevertheless, high quality sequencing of the Spike gene will provide information on any relevant RBD mutations that could impact binding of one or both nMAbs.

**Hypothesis:** The relative benefit of AZD7442 (vs placebo) is larger for those infected with virus without mutations at binding-relevant positions compared with those with such virus mutations.

#### *Statistical Analyses:*

It is expected that the rate of viral variants that contains mutations at the binding-relevant positions is low, with correspondingly low power for statistical tests. For individual mutations that occur at sufficiently high rates, and pooled across mutations, subgroup analyses will be performed comparing AZD7442 versus placebo within subgroups by the presence versus absence of the mutations. The treatment effect will be compared across subgroups by testing for an interaction between the treatment and subgroup indicators. Subgroup analyses will be performed for time to sustained recovery and key safety outcomes, as described above; statistical methods are described in section 8.4 of this SAP. Models will include vaccination status and supplementary oxygen requirements (categories of the ordinal pulmonary outcome) at baseline as covariates.

These are exploratory analyses. In addition, if mutations on other sites occur with sufficient frequency, similar analyses will be performed to identify mutations that are associated with the outcome of the treatment.

## E-9 Missing Outcomes and Missing Baseline nAb Status

Missing primary outcome results and 90-day survival status due to withdrawal of consent or loss to follow-up will be summarized by treatment group, and tests will be performed whether the proportion of missing data is independent of the treatment assignment. Baseline factors related to these missing outcome data, overall and for each treatment group, will be determined using logistic regression. Candidate baseline factors for this investigation include, but are not limited to, categories of oxygen requirement (pulmonary outcome), antigen levels, and the disease progression risk score (section 13.2). Summaries of missing outcome data will also include when patients with missing data were last seen and their last known clinical status (e.g., discharged, hospitalized, alive at home).

As sensitivity analyses, multiple imputation may be used to estimate missing outcomes. Other sensitivity analyses may also be considered following unblinding when the final extent of missing data is known and the pattern of missing data is investigated. As of December 28, 2021, 6 participants had withdrawn consent and 23 additional patients had unknown sustained recovery status at 90 days. Follow-up is ongoing, including attempts to reach patients who are lost to follow-up. Thus, these numbers are likely to change.

We anticipate that 30-60 participants will not have a baseline specimen that can be used to determine nAb status. The primary analysis in the nAb-negative subgroup will be restricted to participants with known (nAb-negative) status, while the total cohort will include both, participants with known and unknown antibody status. As a sensitivity analysis, we will impute nAb status for these participants using baseline characteristics that include age, oxygen requirements, duration of time between symptom onset and randomization, and SARS-CoV-2 vaccination status. Using a logistic regression model, baseline predictors of nAb status will be determined. The coefficients from the regression model will be used to classify the participants with missing nAb status as negative or positive. For the imputation of the missing nAb status, a range of cut-points will be used: participants will be imputed as nAb-negative if the predicted probability of having been nAb-negative at baseline is 50% or greater, 60% or greater, and 70% or greater. The primary comparison for the sustained recovery endpoint in the nAb-negative subgroup will be repeated including both those with known nAb-negative status as well as those who were imputed as nAb-negative, in separate analyses for each of the three imputation cut-points.

## Appendix F. Antibody, Antigen, and viral RNA Assays and Outcomes

SARS-CoV-2 antibody and antigen levels were measured in plasma specimens collected at baseline (Day 0), Day 1, Day 3, and Day 5. Antibody and antigen levels were determined centrally, by the Frederick National Laboratory, blinded to treatment group.

### Antibody Levels

SARS-CoV-2 plasma antibody levels were measured using two assays:

- Levels of neutralizing antibodies (**nAbs**) directed against the SARS-CoV-2 receptor binding domain (RBD) were determined using the **GenScript** SARS-CoV-2 Surrogate Virus Neutralization Test (sVNT) assay (GenScript, Piscataway, NJ, USA).
  - Levels of nAbs reported as “percent binding inhibition”. Specimens with levels  $<30\%$  are considered nAb negative, levels  $\geq 30\%$  are considered positive for nAbs (30% is the manufacturer’s cutoff for positivity).
- **BioRad** Platelia SARS-CoV-2 Total Ab assay (BioRad, Hercules, CA, USA), measuring total (IgA, IgG, and IgM) anti-nucleoprotein (**Anti-N**) antibodies.
  - Results of this antibody measurement are reported as “specimen ratios”. Specimen ratios are defined as the specimen optical density (OD) divided by the optical density of the cut-off control R4 ( $OD_{MR4}$ ). According to the manufacturer, specimen ratios less than 0.8 are considered negative, those with a specimen ratio between 0.8 and 1.0 are considered equivocal, and those  $\geq 1.0$  are considered positive for the presence of antibodies.
  - Equivocal BioRad antibody levels will be combined with negative levels for all analyses unless otherwise stated.
- **Quanterix** anti-Spike IgG semi-quantitative antibody assay (Simoa® Semi-Quantitative SARS-CoV-2 IgG Antibody Test, Quanterix, Bellerica, MA, USA).
  - Automated paramagnetic microbead-based immunoassay intended for qualitative and semi-quantitative detection of IgG antibodies to SARS-CoV-2 in human dipotassium EDTA plasma using the Quanterix HD-X immunoassay system.
  - Functional LLoQ of 82 ng/mL
  - Antibody-positive defined as  $\geq 770$  ng/mL per manufacturer’s recommendation (“clinical cut-off”)
  - The performance of the assay has not been established in individuals that have received a COVID-19 vaccine

**Comment:** For the purpose of comparing natural immunity and whether nMAbs have potential benefit in those with such, the GenScript assay will be used. This attempts to quantify neutralizing antibody titers, whereas the BioRad assay captures any type of anti-N antibody (against a section of virus not causing neutralization).

### Plasma Antigen Levels

SARS-CoV-2 nucleocapsid antigen levels were determined in 90  $\mu$ L plasma in duplicate using

a **Quanterix** assay (Simoa® SARS-CoV-2 N Protein Advantage, Quanterix, Bellerica, MA, USA). The lower limit of quantification for the assay is 3 ng/L.

- Antigen levels < 3 ng/L are considered “antigen negative”.

**Comments:**

- When analyzed as continuous variable, Quanterix antigen levels <3 will be set to 2.9 ng/L.
- When analyzed as continuous variable, antigen levels will be  $\log_{10}$ -transformed.

**SARS-CoV-2 Viral RNA** was assessed at baseline from mid-turbinate nasal swabs.

Qualitative and quantitative assessments of the SARS-CoV-2 RNA in viral transport media (proxy for viral load) by RT-PCR were made centrally by ABML.

- *Qualitative RT-PCR analysis:* Extraction, master mix preparation, and RT-PCR were performed as described in the CDC 2019-Novel Coronavirus Real-Time RT-PCR Diagnostic Panel. RT-PCR was performed on an Applied Biosystems QuantStudio 7 Flex. Ct scores <40 for both nCoV N1 and nCoV N2 probe sets are scored as positive for the presence of SARS-CoV-2 RNA.
- *Quantitative RT-PCR analysis:* Quantitative RT-PCR analysis of the samples used the same RNA extracts prepared for the qualitative assay. Assay conditions were the same as outlined in the CDC protocol except the RNaseP probe was not used.

**Comments:**

- For subgroup analyses, RNA levels in viral transport media will be categorized as (<10,000 cp/mL [low] versus >10,000 cp/mL [high]); the cut-point is close to the median viral RNA level in the TICO bamlanivimab trial. Indeterminate levels will usually be combined with negative levels for analyses.
- When analyzed as continuous variable, RNA levels will be  $\log_{10}$ -transformed.

## Appendix G. Modifications to the Statistical Analysis Plan for MP0420

### Investigational Agent

Appendix H5, version 2.0 (09 April 2021) of the TICO protocol describes agent-specific protocol elements for MP0420 which is being developed by Molecular Partners and Novartis. MP0420 is multi-valent DARPin® molecule consisting of 5 DARPin® domains. MP0420 simultaneously and specifically binds to 3 epitopes of the receptor-binding domain of the SARS-CoV-2 spike protein with three different domains and to human serum albumin with two domains.

### Analysis Population

Treatment comparisons for efficacy and safety outcomes will be by modified intention-to-treat (mITT). The mITT analysis is restricted to participants who received a complete or partial infusion of MP0420/placebo; participants who did not receive any MP0420/placebo are excluded. The TICO platform protocol specifies ITT for the efficacy analyses “unless otherwise stated”, and mITT for safety analyses.

*Justification for changing the study population to mITT for efficacy analyses:* In the TICO trial of MP0420, 496 participants were randomized (ITT population). Of these, 485 were infused (complete or partial) with MP0420/placebo and 11 were not. Of the 11 participants not infused, 9 withdrew consent prior to infusion. Follow-up data after Day 0 was collected for the 2 participants not infused, but remained consented. Because the treatment assignment was blinded, the risk of bias due to restricting analyses to the mITT cohort is low. With this approach, the risk and benefits of MP0420 will be evaluated in the same population.

**Comment:** Investigators were unblinded to summaries of the infusion status of participants, pooled across treatment groups. These analyses were included in the open DSMB reports.

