### **Sample size**

This phase III trial is planned to provide 90% power to detect a 25% increase in the rate of sustained recovery for an investigational agent compared to placebo at the 0.025, 1-sided level of significance. This requires 843 primary events (i.e., participants who achieve sustained recovery). Randomization of 1,000 participants, equally allocated to each investigational agent and placebo, followed for 90 days is estimated to result in the required number of primary events. The event target may be achieved earlier if more than 1,000 participants are enrolled. Sample size will be evaluated periodically by study team members who are blinded to interim results on treatment difference and may be increased to maintain power for the hypothesized difference in sustained recovery between the investigational agent and placebo.

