## **1.3 Randomization**

The randomization is described in section 6.1 of the protocol.

Patients will be equally allocated to each investigational agent + SOC or to placebo + SOC. For example, for a study of a single investigational agent, participants will be randomized in a 1:1 ratio to the investigational agent or placebo. If a patient is eligible for two investigational agents and the placebo can be shared, the allocation will be 1:1:1 to investigational agent A, agent B, or placebo. Because the two investigational agents (A and B) may require different placebos

(for example, when infusion volumes differ), the 1:1:1 allocation ratio will be achieved through a two-step randomization procedure: in *step 1*, the participant is randomized 2:1 to “active” versus “placebo”; in *step 2*, the participant is randomized 1:1 to A versus B. With  $k$  agents, this can be viewed as an initial  $k:1$  allocation to “active” versus “placebo”, followed by a second, even allocation to one of the available agents (for example, if a participant was allocated to “placebo” in *step 1*, then the *step 2* allocation will be 1:1 to “matched placebo for A” versus “matched placebo for B”). For the analysis, the concurrent agent-specific placebo groups will be pooled, resulting in a 1:1 allocation ratio for comparing each investigational agent versus the (pooled placebo) control group. If investigational agents are added or dropped, the allocation ratio to active versus placebo will be appropriately modified, and sample size will be recalculated as appropriate.

Randomization will be stratified by study site pharmacy (several clinical sites may share one pharmacy) and severity of disease at entry; the two disease severity strata are defined in section [1.2](#) of this SAP.

If more than one investigational agent is being compared with placebo and they have different contraindications, it is possible that a participant is eligible only for a subset of agents.

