## 1.4 Sample Size Estimates

The planned sample size for each pairwise comparison is 1,000 participants (500 participants in each group). The sample size is sufficient to detect a recovery rate ratio (RRR) of 1.25 for time to sustained recovery with 90% power, using a one-sided test with a significance level of 0.025. The treatment groups are compared using Gray’s test with  $\rho=0$ , the competing risks analogue of the log-rank test.

Sample size calculations are described in detail in Section 6.3 of the protocol.

Blinded sample size re-estimation will be carried out before enrollment is complete to determine whether the planned sample size of 1,000 participants followed for 90 days will yield the planned number of 843 primary events. The blinded sample size re-estimation does not involve unblinding of the treatment difference. It will be based on the pooled outcome data. Sample size may be increased to achieve the event target in the planned follow-up of 90 days. A

sample size increase may also be considered in order to achieve the event target before all participants are followed for 90 days.

When 300 participants (150 per study arm) are enrolled and have Day 5 outcome data, an early futility assessment is planned. This assessment will be based on two ordinal outcomes, denoted as “pulmonary” and the “pulmonary+”; both are ordered categorical outcomes with 7 categories, assessed on Day 5 (the two outcomes are described in [Appendix A](#)). Treatment groups will be compared using proportional odds models. With 300 participants, the early futility assessment is powered to detect a summary OR=1.60 with power of 95%, using a one-sided test with significance level of 0.30. Given the two-outcome decision rules, an investigational agent with a summary OR=1.60 at Day 5 for both outcomes, would pass the futility assessment with a power between 93% and 98%, and a type I error between 0.21 and 0.39.

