### **Assessment of model assumptions**

- The trial was powered to detect an RRR of 1.25 with 90% power; this requires 843 sustained recoveries among the 1000 participants by Day 90. The rate of recoveries will be monitored, overall and within the two disease severity strata. Deviations of the observed distribution from the hypothesized distribution in the control arm will be monitored, and the impact on the power of the trial will be assessed. Prior to the completion of the trial for the investigational agent, sample size will be re-estimated by the blinded statisticians on the study team, based on the pooled rate of *sustained recovery*.

- The Fine-Gray model assumes that the sub-distribution rate ratio for *sustained recovery* is constant over time, similar to Cox proportional hazards models. The assumption of constant RRR will be tested by including an interaction effect between time and treatment indicator.

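### The platform's 1,000 participants, 843 recoveries and 90% power are left unmodified for MP0420, but its cohort of 485 to 496, if final, cannot reach 843 events and gives about 62% power

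*SAP*

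**What the plan says.** The size and power are set once for the platform. SAP section 1.4: "The planned sample size for each pairwise comparison is 1,000 participants (500 participants in each group"). Section 8.1, in the part that checks the model: "The trial was powered to detect an RRR of 1.25 with 90% power; this requires 843 sustained recoveries among the 1000 participants". Section 10.3 uses the same 843 as the denominator of the information fraction for the efficacy boundary.

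The agent-specific paragraph of section 1.2 says that departures from the platform design, such as a changed sample size, are set out in the agent appendices. Appendix E does this for AZD7442. It gives a new event target of 1,228 (E-2), power recomputed from pooled events before unblinding (E-3) and a changed information denominator (E-6).

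Appendix G covers MP0420. It moves the efficacy analysis to mITT and adds rash summaries and subgroup analyses. In justifying mITT it states: "In the TICO trial of MP0420, 496 participants were randomized (ITT population"), of whom 485 were infused and 11 were not. It gives no event target, pooled event count, power, detectable RRR, information denominator or reason for the smaller size.

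**The concern.** Since Appendix G changes none of the platform figures, the 90% in sections 1.2, 1.4 and 8.1 is the only power statement in the SAP that a reader can apply to MP0420. The reported cohort is about half the planned one. Someone reading a non-significant MP0420 result beside that 90% would think a 25% improvement had been tested with a 1-in-10 chance of being missed. On the cohort reported, the chance of missing it is nearer 4 in 10.

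The level of the final test is also open. If the agent did not run to 843 events, the SAP does not say how much of the one-sided 0.025 is available at the final analysis, or against which denominator.

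**Working it through.** **Inputs**
- Effect: RRR 1.25 with 90% power (SAP sections 1.2 and 1.4).
- Level: "at the 0.025, 1-sided level of significance" (section 1.2, Sample size).
- Allocation: "resulting in a 1:1 allocation ratio for comparing each investigational agent versus the (pooled placebo) control group" (section 1.3).
- Events: "This requires 843 primary events (i.e., participants who achieve sustained recovery") (section 1.2, Sample size).
- MP0420 cohort: 496 randomized, 485 in the mITT efficacy population (Appendix G).
- Recovery proportion: not given for MP0420, so assumed. The plan implies 843/1,000 = 84.3%; AZD7442 had 1,195/1,417 = 84.3% (Table E-1). Shown over 75% to 100%.

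**Step 1. Reproduce the plan's figures.** Gray's test with rho = 0 is treated as a log-rank test with 1:1 allocation (Schoenfeld):

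d = 4(z₀.₉₇₅ + z₀.₉₀)² / (ln 1.25)² = 4(1.960 + 1.282)² / (0.2231)² = 844.1

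This agrees with 843, and power at 843 events is 90.0%. The same formula gives detectable RRRs of exp(2 × 3.242/√1195) = 1.206 at 90% power and exp(2 × 2.802/√1195) = 1.176 at 80%. Both match Table E-2, so the method is consistent with the SAP's own.

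**Step 2. Ceiling on events.** With at most one recovery per participant, MP0420 can yield at most 485 events by mITT (843 − 485 = 358 short) or 496 by ITT (843 − 496 = 347 short).

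**Step 3. Power for RRR 1.25.** Power = Φ(√d/2 × ln 1.25 − 1.960), using the full one-sided 0.025.

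| Recovery among 485 | Events | Share of 843 | Power |
|---|---|---|---|
| 75% | 364 | 43.2% | 56.7% |
| 80% | 388 | 46.0% | 59.4% |
| 84.3% | 409 | 48.5% | 61.7% |
| 90% | 436 | 51.7% | 64.4% |
| 100% (ceiling) | 485 | 57.5% | 69.1% |

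Worked line for 409 events: √409/2 × 0.2231 − 1.960 = 2.256 − 1.960 = 0.296, and Φ(0.296) = 0.617. With all 496 randomized, 84.3% recovery gives 418 events and 62.6% power, and the ceiling is 70.0%.

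**Step 4. Detectable RRR at 409 events.** exp(2 × 3.242/√409) = 1.38 at 90% power; exp(2 × 2.802/√409) = 1.32 at 80%.

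**Step 5. Why the final level must be stated.** Suppose the section 10.3 spending function, with denominator 843, were applied at 409 events with no earlier look. Then t = 409/843 = 0.485, and the level spent is 2[1 − Φ(2.241/√0.485)] = 0.0013 one-sided (Z about 3.01). Power for RRR 1.25 would be Φ(2.256 − 3.013), about 22%. The SAP does not say that this would be done. The figure shows only how far the result depends on a point that Appendix G leaves open.

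**The case against.** The strongest reply is that 1,000, 843 and 90% are planning figures, worded as such, and that the plan allows an agent to finish below them. Section 1.2 (Monitoring) provides for unblinding and reporting after an early stop. Section 10.2.1 allows randomization to stop at the early futility review. Section 14 allows earlier unblinding on the DSMB's recommendation. This stands. A reader might infer that 496 contradicts the design, or that the trial broke its own rules. The documents do not support either inference.

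Four further points stand in part.

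- No text says that 496 is final or why enrolment ended. The past tense and the ITT label suggest it is final. The MP0420 protocol appendix (H5) and section 6.3 of the master protocol, both cited in the SAP, are not among the documents reviewed and may record the reason. The gap shown here is in the SAP, whose section 1.2 nevertheless places such changes in the agent appendices.
- The 409 events rest on a borrowed recovery proportion. That moves the power between 57% and 69% but does not restore 90%.
- The AZD7442 parallel is imperfect. Its power was reassessed after a deliberate increase in target, and the result fed a new two-hypothesis analysis. No rule requires every agent appendix to restate power. Still, E-3 reassessed power for a shortfall of 33 events, whereas the shortfall here is at least 347 by either population.
- A reader might infer that the SAP would treat a non-significant MP0420 result as proof of no effect. It does not say that. Section 8.1 already calls for the RRR with a 95% CI, and section 9.1 already warns of limited power in subgroups. No extra interpretation rule or subgroup power figure is needed.

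**Conclusion.** The point holds as an unreconciled statement of size and power, not as an arithmetic contradiction. If 496 is final enrolment, the 843-event target is out of reach for MP0420 whatever the recovery rate, and 90% power for RRR 1.25 does not apply to it. Power is about 62% at the planned recovery proportion, 57% to 64% for 75% to 90% recovery, and no more than 69% in the mITT population. These figures assume 1:1 allocation, a log-rank approximation to Gray's test and the full one-sided 0.025 at the final analysis. The ceilings do not depend on the borrowed recovery proportion; the 62% does.

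**What to change.** Before MP0420 is unblinded, add to Appendix G a short statement parallel to E-3 that:

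- says 1,000 participants, 843 events and 90% power do not apply to MP0420;
- gives the enrolment status and the reason enrolment ended;
- gives the actual pooled number of sustained recoveries;
- gives, from that count, the power for RRR 1.25 and the RRR detectable at 80% and 90% power (about 1.32 and 1.38 if the count is near 409);
- states the significance level and the information denominator for the final test.

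Use the observed count. Do not write in the 409 events, which rest on an assumed recovery proportion, or nAb-negative subgroup figures borrowed from AZD7442. Section 2 already provides for giving pooled event numbers to the blinded statisticians for sample size re-estimation, so the count can be had without unblinding treatment comparisons. The cost is one paragraph and a small table, with no further participants and no change to the analysis.
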